Early Palliative Care and Hematological Cancer Patients: a Phase II Study

NCT number: NA

Date: May , 15th , 2018

Research protocol on early palliative care and hematological cancer patients: a phase II study.

Introduction

The most recent World Health Organization (WHO) definition of palliative care advocates that palliative care principles "...should be applied as early as possible in the course of any chronic, ultimately fatal illness." (Sepulveda 2002). The difference with the previous WHO vision was substantial, as the earlier definition recommended Palliative Care to patients not responsive to curative therapy, limiting its role to the last period of life.

Evidence about the effectiveness of an early integration of palliative care has begun to emerge in the last years, primarily for cancer patients. The results of experimental studies (Temel 2010; Zimmermann 2014; Higginson 2014), showed the effectiveness of early integration of palliative in the management of advanced illness, in improving quality of life (Temel 2010; Higginson 2014), reducing consumption of resources (Temel 2010), and possibly increasing survival (Temel 2010; Higginson 2014). These data were also confirmed in Italy (Maltoni 2016, Costantini 2017).

Hematological advanced patients suffer from a very high symptoms burden, psychological, spiritual, social and physical symptoms. They are very similar to oncological advanced patients (Manitta 2011; Le Blanc 2015). Hematologic patients during the last 30 days of their life are more frequently admitted in Hospital setting, emergency departments and high care ward than oncological patients, they received more aggressive treatments and more chemotherapy or biologic active treatments than oncologic patients (Hui 2014)

Looking to WHO's palliative care definition and hematologic patients' symptoms burden it's simple to imagine that an early access to palliative care service could be the answer, as it was for advanced oncologic patients. The rationale of the new vision lied on the recognition that palliative care had the potential to improve quality of life of patients and their family members during the whole trajectory of an incurable disease, through an effective management of psychological and physical symptoms, appropriate relationships, effective communication and support in decision-making.

In addition, even if WHO definition is referred to incurable patients, recent experience on Palliative care and Hematology is also about potentially curative patients. (Roeland 2015, Barbaret 2018).

Nonetheless, access to palliative care in hematologic patients care results totally absent or confined

in the last days of life (Howell 2011; Corbett 2013). There is a resistance by hematologic specialists to address patients to a palliative care service because of the possible misunderstanding between active treatment and palliative care assistance, identified from many professionals as terminal care (Auret K 2003)

A call to a new model of integration between palliative care and hematologic service is strong (Bandieri E 2013); for some authors just from the beginning of an advanced disease (Odejie 2016) and for other authors modelled on the different patients' needs (Manitta 2010, Tuca 2017)

The aim of the study is to pilot a new model of integration for advanced hematological cancer between hematological and palliative care. Eligible patients will be at the last active treatment (chemotherapy or immunotherapy) as decided by hematologists.

The primary aim is to evaluate the feasibility, acceptability and efficacy of this novel intervention.

The evaluation procedure will be evaluated for feasibility and applicability

To our knowledge this is the first trial on an integrative model between palliative care and hematology for an advanced hematological population.

Primary aim

To evaluate the feasibility of integrated versus standard involvement of palliative team for hematological advanced patients.

Secondary aims

- ✓ to evaluate the efficacy of this new model on Quality of Life (QoL) until 6 months after the enrollment.
- ✓ to evaluate the impact of the intervention on care pathways (number of chemotherapies in the last 30 days, number of exams, length of stay in Hospital or Hospice, access to emergency department, setting of death and so on)
- ✓ to evaluate the acceptability of the intervention by patients, professionals and caregivers.

Methods

Study design

This is a randomized control trial, phase II, systematic versus on demand palliative care

The eligible patients, after providing consent, will be randomized:

- A. Experimental arm. Patients in this arm will meet with the palliative care team soon after the decision on their last active treatment
- B. Standard arm. Patients in this arm will meet palliative care team at the discretion of their hematologist or at their request

The study was defined as a complex intervention according to MRC framework (Campbell 2000; Campbell 2007). It is a mix method phase II study.

Population

The study will enroll 60 patients, both inpatients and outpatients as established in inclusion criteria. Additionally, the study will include 6 caregivers, 6 patients and 6 professionals for the qualitative interviews.

Inclusion Criteria

- Histologically or cytologically confirmed incurable hematological tumor
- Estimated prognosis by the hematologist more than 1 month at least
- Predictive last active treatment (chemotherapy or immunotherapy) as established by hematological equipe.
- 18 years old;
- ECOG ≤ 3 ;
- Ability to read and respond to questions in Italian;
- Consent to the study

Exclusion criteria

- Existence of other co morbid disease which in the opinion of the investigator prohibits participation in the protocol
- Caregiver's absence

Participants will be recruited from a Hospital Hematology department. Participation in the study will be strictly voluntary. Hematologic physicians and palliative care physicians identify eligible patients during weekly cases' discussion in the Hematological department. A research nurse will give to each eligible patient a description of the study. The referring hematologist will obtain written informed consent prior the randomization. Once a patient has been consented an external researcher will submit the questionnaires before randomization.

Study participants will be randomized from the statistical department in a 1:1 fashion to the integrated or standard palliative care intervention. Participants who are randomized to the integrated arm will meet the palliative care team before starting the last active treatment. Participants randomized to standard palliative care will be evaluated and followed by the palliative care team at the discretion of their treating hematologist or at their request.

Palliative Care intervention

Palliative care intervention is realized by professionals trained nurses and physicians who provide care and support in inpatients and outpatients setting.

This Palliative care service, defined as “Specialist Palliative Care Team” (SPCT), may include, as established by systematic reviews on this topic (Higginson 2003; Gomes 2009):

- a. two or more professionals fully involved in SPCT;
- b. at least one of them with a specialized degree in palliative;
- c. palliative care for both inpatient and outpatient setting

In this study, the palliative care intervention will guarantee by Palliative Care Unit. Two physicians and two nurses constitute the Unit. Psycho oncologic unit can be involved for more complex clinical cases.

The initial assessment will occur in the outpatient clinic or in the ward as consult. Anyway, it will be achieved before the starting of the last active treatment. Once patients are discharged from the hospital they will be followed outpatients pursuant to the study guidelines.

The SPCT will follow each patient on regular basis in conjunction with his or her primary hematologist. Professionals or patients and their families will arrange additional visit at their discretion.

Palliative care team and treating hematologists will discuss active patients issue to assure a team approach to the patient’s care. They participate to the weekly cases’ discussion in Hematology department. In case of urgent and important issue they discuss each patient by telephone or planning clinical encounter together.

Palliative care service will follow the outpatients until is possible. The assistance will be interrupted for patients deny, death or any causes could make impossible the ambulatory assistance.

Standard palliative care intervention

Patients randomized to the standard palliative care arm will be seen by the SPCT at the request of their hematologist at any time. The care will not be standardized but planned on patients ‘needs.

Evaluation pattern and instruments

The study considers a qualitative and a quantitative evaluation.

Quantitative evaluation

Primary endpoint

Feasibility will be collected on the % of randomized patients who will follow the palliative care program during the 3 months after the enrollment

Secondary Endpoints

1. The efficacy on QoL during the follows 6 months will be assessed by

- POS (Palliative Care Outcomes Scale)
- ESAS (Edmonton Symptom Assessment System)
- HADS (Hospital Anxiety and Depression Scale)
- ECOG (Eastern Cooperative Oncology Group)

Palliative Care Outcome Scale (POS; Hearn & Higginson, 1999): (POS) is a widely used, validated also in Italy (Costantini et al 2016), brief outcome measure, used in in-patient, community and outpatient settings among patients with advanced illnesses. The original English version of the POS comprises 10 items, including physical and psychological symptoms, spiritual and emotional dimensions, communication with patients and families and practical concerns related to stage of disease. The POS also includes an open optional question to list the main concerns. Each of the 10 items is scored with a Likert scale ranging from 0 to 4.

The ESAS (ESAS; Bruera et al., 1991) instrument asks respondents to rate the severity of 10 common symptoms (pain, fatigue, nausea, depression, anxiety, drowsiness, shortness of breath, appetite, sleep, and feeling of well-being) during the previous 24 hours. This questionnaire has been found to be valid and reliable in cancer populations.

Eastern Cooperative Oncology Group (ECOG Performance Status; Oken et al., 1982): the ECOG performance status is a scale used to assess how a patient's disease is progressing, assess how the disease affects the daily living abilities of the patient, and determine appropriate treatment and prognosis

- grade 0: fully active, able to carry on all pre-disease performance without restriction
- grade 1: restricted in physically strenuous activity but ambulatory and able to carry out work of a light or sedentary nature, e.g., light housework, office work
- grade 2: ambulatory and capable of all self-care but unable to carry out any work activities, up and about more than 50% of waking hours
- grade 3: capable of only limited self-care, confined to bed or chair more than 50% of waking hours
- grade 4: completely disabled, cannot carry on any self-care, totally confined to bed or chair
- grade 5: dead

The HADS (HAD R.P. Snaith and A.S. Zigmond, 1983) is a self-assessment 14-item questionnaire which has been well tested in cancer patients. It has two 7-item subscales assessing depression and anxiety in the preceding week. The scale is considered appropriate for cancer patients because of the lack of items regarding somatic symptoms, which can confound the identification of psychiatric issues. The format consists of four responses (0-3) that quantify the degree to which a particular emotion is experienced by the patient. The score on each subscale ranges from 0 to 21 and a score

of greater than 11 is considered to be consistent with definitive depression or anxiety. A score of less than 7 is normal and a score of 8–10 is considered borderline for depression and anxiety

2. the efficacy on health processes and procedures will be collected by indicators recoverable in electronic data base (see session below)

The quantitative assessment

We consecutively register all eligible patients (and reasons for ineligibility) both from Hematological department, patients who were asked to participate to the study (and reasons for not), patients who accepted to participate (and reasons for not).

We register all visits with the patients (outpatient visits and consultation during hospital admissions) and with family members. We collect from medical records information about hospital and emergency admissions, anticancer chemotherapies (drugs and date of administration), referral to community PC services (domiciliary PC teams and inpatient hospices), date and place of death, overall survival.

Three questionnaires will be proposed to the patients for self-assessment by 2 trained researches after the consent (T0), at 4 weeks (± 7 days) after t0 (t1), at 8 weeks (± 7 days) after t0 (t2), at 12 weeks (± 7 days) after t0 (t3), at 16 weeks (± 7 days) after t0 (t4), at 20 weeks (± 7 days) after t0 (t5) and at 24 weeks (± 7 days) after t0 (t6)

Once the questionnaires will be submitted in Hospital and then depending on patients' preferences for the following evaluations (at time 1 (t1) to time 6 (t6)).

The Quantitative assessment (questionnaires and information from medical records) will be collected for both the arms, experimental and standard one

Statistical methods

The feasibility of the early integrated PC intervention was assessed estimating the proportion of

hematologic patients who accepted to participate in the intervention and attended the first PC visit. We plan to recruit 60 study participants. The feasibility will be achieved if >50% of patients remain in the program in the next 3 months from the enrollment

It will be possible to assess the feasibility of the experimental intervention assuming 5% as level of significativity and 80% as statistical power on the basis of the subsequent hypotheses:

- 1) planned statistical test: chi-squares with 1 degree of freedom;
- 2) type of comparison: 2 tailed;
- 3) p-value calculation mode: exact (because the small sample size);
- 4) alternative hypothesis: 75%;
- 5) allocation ratio: 1:1.

(Power analysis was performed using nQueryAdvisor, sheet POT0x, version 7.0).

To reach the primary objective, the statistical test as cited at point 1 will be used according to specification better detailed at point 2 and 3; about the tested percentage, the exact two-sided 95% confidence interval will be calculated according to the Clopper-Pearson approach.

About the secondary objectives, each score related to the PRO tools (POS, ESAS, HADS, ECOG) will be assessed in terms of temporal evolution and differences between the two arms using GEE models. Furthermore, within each arm and for each observational time, it will be calculated (for each score):

- the mean with its 95% two-side confidence interval (assuming asymptotic normality for the related estimator);
- common descriptive statistics (minimum, maximum, main percentiles, standard deviation).

The same approach will be followed for each change measure vs baseline, where such kind of change has to be intended in terms of difference between the score value at the time of interest and the related value at baseline.

If it will be deemed useful, such change measures can be depicted in relative way (eg, as percentage vs the related baseline value).

Statistical analyses will be performed by staff of Clinical Trials and Statistics Unit. To this aim, SAS System or R will be used according availability and version in use.

Qualitative assessment

Consent to the qualitative assessment will be requested to a consecutive series of six patients and six family members (from patient's others than previously selected) who would attend at least three visits in the PC outpatient clinic. A qualitative assessment will also be proposed to a sample of six physicians involved in the care of patients recruited in this study, selected among those who will follow the highest number of patients.

Information will be gathered through three individual semi-structured interviews exploring the experience of the different 'actors' of the intervention, i.e. the receivers (patients and family members) and the physicians involved in the early integrated palliative care.

Interviews address to patients and family members focused on perceived benefits and concerns of the early PC intervention, with reference to the main domains which informed its structure. Interview address to physicians focused on exploring strengths and weaknesses of the intervention with reference to both the respondents' view on patients' and family caregivers' experience, and their own role (including specific tasks required to them) within the study.

A member of the research team with expertise in qualitative evaluation in palliative care develop the topic guide of the interviews. If the identified participant agrees with the evaluation, an interviewer contact him/her. Anonymity and non-traceability criteria will be duly presented to all interviewees. Explicit permission is requested for the interview to be audio-recorded. Interviewers are two nurses with expertise in palliative care, with basic knowledge of the intervention but not involved in its implementation.

Data analysis

Tape recordings of the interviews are transcribed verbatim, and then analyzed using thematic

analysis to explore the content and context of responses (Payne et al 2007).

In the first step, one researcher develops coding schemes covering themes congruent with the structure of the interview topic guides. Then two researchers independently analyze the transcripts and categorized all segments of the text potentially relevant to the interview topics. Throughout an iterative process, they inductively identify a number of subthemes. In the second step, the two researchers compare the categorizations, and reconsider and discuss any differences in interpretation in order to reach an agreement, and to develop a unique preliminary categorization. Finally, a third researcher revise both the transcripts and the preliminary categorization, regroup and rename some themes and subthemes with the objective of describing them through highlighting commonalities and differences between the perspectives of the three 'actors' enquired. This revision will be discussed and emended with the other researchers involved in the qualitative analysis.

Ethics

The study protocol has been approved by the Ethics Committee. No financial compensation will be provided to the participants in the study. In accordance with good clinical practice patients will be informed about participation in the study and its implications. Written consents will be obtained

Conclusions

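### The feasibility success sentence is not tied to the planned exact test: read literally it is met at 16/30, while the test, on an inferred 50% null and 30 patients, needs 21/30

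*Combined protocol and SAP*

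**What the plan says.** In the combined protocol and SAP, Statistical methods gives the success rule in one sentence: "The feasibility will be achieved if >50% of patients remain in the program in the next 3 months from the enrollment". It mentions no test, p-value or confidence limit.

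The next sentence sets the error rates: "It will be possible to assess the feasibility of the experimental intervention assuming 5% as level of significativity and 80% as statistical power". The list below it specifies a chi-square test with one degree of freedom, two-tailed, with exact p-values and 1:1 allocation. Its fourth item is "4) alternative hypothesis: 75" (per cent). The section then assigns this test to the primary endpoint: "To reach the primary objective, the statistical test as cited at point 1 will be used". For the tested percentage, "the exact two-sided 95% confidence interval will be calculated according to the Clopper-Pearson approach".

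Three things are not written anywhere: the null value, a cut-off count, and a statement that significance is needed to declare feasibility.

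The denominator is also open. Under Primary endpoint, "Feasibility will be collected on the % of randomized patients who will follow the palliative care program during the 3 months after the enrollment", with no arm named. Patients in the standard arm "will be seen by the SPCT at the request of their hematologist at any time", according to the section on standard palliative care.

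Statistical methods also describes feasibility in a second way, as the proportion of "hematologic patients who accepted to participate in the intervention and attended the first PC visit", without relating this to the 3-month endpoint.

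**The concern.** A prespecified success rule should give one answer for each possible result. Here there are two candidates. One is an observed proportion above one half. The other is rejection of a null, presumably 50%, by an exact two-sided 5% test. They part company over a range of plausible results, and the plan does not say which governs.

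The 5% error rate that the plan states belongs to the test. A bare majority of a small sample does not carry it. If the success sentence were applied as written, the study could be reported as having shown feasibility on a result that is fully compatible with retention below 50%. Choosing between the two readings after seeing the data is what a prespecified rule is meant to prevent.

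**Working it through.** **Inputs.** From Statistical methods: 60 patients, 1:1 allocation, two-sided 5%, power 80%, alternative 75%, exact p-values. Inferred: null p0 = 50%, taken from the success sentence; n = 60/2 = 30, because the sizing refers to the experimental intervention and the standard arm is seen on request; and a one-sample test.

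**Step 1: reproduce the stated power.** With X ~ Binomial(n, p), find the smallest r with 2 × P(X ≥ r | p0 = 0.5) ≤ 0.05. Power is then P(X ≥ r | 0.75).
- r = 20, n = 30: 2 × 0.04937 = 0.0987, not significant.
- r = 21, n = 30: 2 × 0.02139 = 0.0428, significant.
- Power = P(X ≥ 21 | 30, 0.75) = 0.8034, against 80% stated.

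Neighbouring sizes fit less well: 0.750 at n = 28, 0.713 at 29 and 0.771 at 31. The asymptotic chi-square gives the same cut-off: (20 − 15)²/7.5 = 3.33, p = 0.068; (21 − 15)²/7.5 = 4.80, p = 0.028.

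**Step 2: test the inferred inputs against alternatives.**
- All 60 patients in one sample, null 50%: cut-off 39/60, power 0.970.
- Two-arm comparison of 50% with 75%, 30 per arm: power 0.517 (pooled normal approximation) or 0.413 (Fisher exact).
- One sample of 30 with a null of 45% or 55%: power 0.894 or 0.514.

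Of these, only a one-sample test of 50% with n = 30 fits the stated 80%.

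**Step 3: compare the two rules at n = 30.** More than 50% of 30 means more than 15, so at least 16.

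| | Success sentence, literal | Exact two-sided test |
|---|---|---|
| Smallest count that succeeds | 16/30 (53.3%) | 21/30 (70.0%) |
| Exact two-sided p at that count | 0.856 | 0.043 |
| Clopper-Pearson 95% CI | 34.3% to 71.7% | 50.6% to 85.3% |
| P(success) at true 50% | 0.4278 | 0.0214 |
| P(success) at true 75% | 0.9973 | 0.8034 |

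At 20/30 the interval is 47.2% to 82.7%, so 50% is not excluded.

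**Step 4: probability that the rules disagree.** This is P(16 ≤ X ≤ 20) = P(X ≥ 16) − P(X ≥ 21).
- True 75%: 0.9973 − 0.8034 = 0.194.
- True 50%: 0.4278 − 0.0214 = 0.406.

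At intermediate values, which the plan does not mention and which serve only as illustration, it is 0.648 at 60% and 0.394 at 70%.

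**Step 5: does the denominator matter?** With all 60 patients the gap remains: the literal sentence is met at 31/60 and the test at 39/60, with disagreement probability 0.030 at a true 75% and 0.435 at a true 50%. This denominator does not fit the stated power.

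**The case against.** The strongest reply is that there is no real conflict. Read together, the success sentence states the claim about the true proportion, and the test decides it. The power statement follows immediately, and the section then assigns the exact test to the primary objective. That a 50% null reproduces the stated power suggests the threshold and the test were built together. On this reading only some labels are missing, and the 42.8% figure describes an analysis that nobody intends. The required interval would in any case show readers of a 16/30 result that 50% is not excluded.

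Most of this stands. It is the likelier reading, and it rules out two stronger inferences that a reader might draw. The first is that the sample size or the 80% power is wrong; the power reproduces. The second is that the trial runs at a false-positive rate of about 43%; that would follow only if the planned test were set aside, which the documents do not say.

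What does not fall away is that the only sentence defining success makes no reference to the test, and the interval is only to be calculated, with no condition on its lower limit. The favourable reading has to be supplied by the reader.

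**Conclusion.** The point holds as an unlinked decision rule. It is not a contradiction in the design or a faulty sample size. On the literal sentence success begins at 16/30; on the planned test it begins at 21/30. The five counts from 16 to 20 are left open, with probability 19.4% if the plan's alternative of 75% is true and 40.6% if true retention is 50%.

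That the link is missing is certain from the text. The 21/30 cut-off rests on three inferences: a null of 50%, 30 experimental-arm patients all kept in the denominator, and a one-sample test. Together they reproduce the stated power, which the alternatives tried do not. The cut-off also depends on the two-tailed test as written; a one-sided 5% exact test would need 20/30 (p = 0.0494).

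A reader might take the 1:1 allocation and the comparative wording of the primary aim to mean a two-arm test. At 30 per arm that would have 41% to 52% power for 50% against 75%, so it is not what was sized under those proportions.

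This should be fixed before analysis, because the ambiguity can reverse the primary conclusion.

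**What to change.** State the null as 50% and the denominator as all patients randomized to the experimental arm. Replace the success sentence with:

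*Feasibility is achieved if the lower exact two-sided 95% Clopper-Pearson limit for the proportion remaining in the program at 3 months exceeds 50% (at least 21/30; recomputed if the denominator differs).*

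With a 50% null this condition agrees with upward rejection by the planned exact test, so rule, test and interval give one answer.

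The cost is a few sentences and no extra patients. Relative to the literal sentence, the bar rises from 53.3% to 70.0% observed retention. The chance of missing a true 75% rises from 1 − 0.9973 = 0.3% to 1 − 0.8034 = 19.7%, which is the risk already accepted by planning for 80% power. Relative to the planned test, nothing changes.

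Separately, the sponsor should reconcile the first-visit proportion in Statistical methods with the 3-month endpoint under Primary endpoint. How deaths within 3 months count is a different question and lies outside this change.

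### The GEE comparison of QoL between arms does not say how the pre-randomization score enters, and large-sample intervals are planned for about 30 patients per arm: a cheap, low-severity improvement

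*Combined protocol and SAP*

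**What the plan says.** All places are in the combined protocol and SAP.

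- **Statistical methods, secondary objectives.** Each score "will be assessed in terms of temporal evolution and differences between the two arms using GEE models". No covariates, role for baseline, working correlation, variance estimator, reference distribution or contrast are named.
- **Same section, summaries.** Within each arm and at each visit the plan reports "the mean with its 95% two-side confidence interval (assuming asymptotic normality for the related estimator"). It adds: "The same approach will be followed for each change measure vs baseline". That sentence follows the per-arm summaries, and it is unclear whether it also reaches the GEE.
- **Statistical methods, sample size.** "We plan to recruit 60 study participants". For the primary test the plan specifies "p-value calculation mode: exact (because the small sample size").
- **Population.** "Study participants will be randomized from the statistical department in a 1:1 fashion", and "an external researcher will submit the questionnaires before randomization".
- **The quantitative assessment.** "Three questionnaires will be proposed to the patients for self-assessment" at T0 and every 4 weeks to week 24, in both arms. I read the three as POS, ESAS and HADS. ECOG is left aside here.
- **Secondary aims.** QoL efficacy over 6 months is the first secondary aim.

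**The concern.** A score measured before randomization cannot be affected by arm, and it usually predicts later scores. Using it as a covariate therefore sharpens the comparison of arms at no cost in data. The plan collects that score but does not say that the GEE uses it in this way. Several models that fit the wording would waste much of its information, and the choice between them is left open until the data are in.

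Two further points come from the size of the trial. Intervals built on normal quantiles are a little too short at 30 per arm, and shorter still as patients are lost; the Conclusions describe a population with limited survival. The usual GEE sandwich variance is also biased downward when there are few patients.

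At stake is the precision, and to a small degree the error rate, of the QoL comparison. The feasibility result is not at stake.

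**Working it through.** **1. The plan's own figure.** The documents give no power for the QoL comparison. The stated 80% belongs to feasibility. It reproduces as a one-sample exact test of 50% against 75% in the 30 experimental patients: success at 21 or more of 30, two-sided exact alpha 0.043, power 80.3%. The 60 patients were thus sized for feasibility, and QoL precision is whatever remains.

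**2. Patients per arm.** 60/2 = 30 as planned. No dropout rate is given. As an assumption, 75% completion at 3 months, repeated, leaves 30 × 0.75² = 16.9, about 17 per arm, at week 24.

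**3. How baseline enters.** Take unit variances. Let V be the variance of the average of the six post-baseline scores (weeks 4-24) and c its covariance with T0. The per-patient variances are:

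- raw post-baseline average: V
- change from baseline: V + 1 − 2c
- T0 as covariate: V − c²

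The covariate model gains c² over raw and (1 − c)² over change. Neither can be negative, so in large samples adjustment is never less precise than either. With T0 as a visit in an unconstrained arm-by-visit model and complete data, the contrast reduces to the raw or the change comparison.

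The correlations are assumed. For constant correlation r, V = (1 + 5r)/6 and c = r. Detectable difference (80% power, 30 per arm) = 2.802 × √(2 × variance/30), in SD units. Power at an assumed 0.5 SD uses a t approximation with 58 df and complete data.

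| Correlation | Variance raw / change / adjusted | Cut vs raw | Cut vs change | Detectable difference | Power, % |
|---|---|---|---|---|---|
| constant 0.5 | 0.583 / 0.583 / 0.333 | 43% | 43% | 0.55 / 0.55 / 0.42 | 70 / 70 / 91 |
| constant 0.6 | 0.667 / 0.467 / 0.307 | 54% | 34% | 0.59 / 0.49 / 0.40 | 65 / 80 / 93 |
| 0.8^lag | 0.680 / 0.696 / 0.438 | 36% | 37% | 0.60 / 0.60 / 0.48 | 64 / 63 / 82 |
| 0.9^lag | 0.824 / 0.418 / 0.330 | 60% | 21% | 0.66 / 0.47 / 0.42 | 56 / 84 / 91 |

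Example, constant 0.6, adjusted: standard error √(2 × 0.307/30) = 0.143; 0.5/0.143 = 3.49; power 93%.

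From unrounded values, the power gain from adjustment is 7-21 points over change and 18-36 over raw. Outside these four structures, the gain over change is 1.5 points at constant 0.8, and the gain over raw is 7.6 points at constant 0.3.

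**4. T0 as a response with the arms set equal at T0.** With an exchangeable working correlation, the variance for the same average is 0.307 (constant 0.6), 0.446 (0.8^lag) and 0.334 (0.9^lag), against 0.307, 0.438 and 0.330 with the covariate. Almost nothing is lost.

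**5. Intervals.** If asymptotic normality means a multiplier of 1.96, coverage for normal data is P(|t with n−1 df| < 1.96): 94.0% at n=30 and 93.2% at n=17. The t-to-normal width ratio is 2.045/1.96 = 1.04 at n=30 and 2.120/1.96 = 1.08 at n=17.

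**6. Sandwich variance, simulated with no arm effect.** With 30 per arm, complete data, exchangeable working correlation and 5,000 trials per cell, the uncorrected sandwich with a normal reference rejects 5.4-6.4% for the week 4-24 average (Monte Carlo error about 0.3 points). A separate simulation of the joint 6-df arm-by-visit test (independence working correlation, 1,500 trials) gives 11.7% uncorrected and 7.1% with the Mancl-DeRouen variance and an F reference (error about 0.9 points near 12%).

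**The case against.** The strongest reply is that this is an unspecified model and not a wrong one. The plan names GEE and leaves the details to its statistics unit, which could add a baseline term and a corrected variance without departing from the text. The request to describe evolution over time also allows T0 to be a response. With the arms constrained equal there, step 4 shows essentially no loss. This stands, and it makes the precision loss conditional.

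Second, the size of the gain rests on correlations and a 0.5 SD effect that the documents do not give. This stands too: over change, the gain is anywhere from 1-2 to about 20 points under the structures tried. The direction does not depend on the assumption.

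Third, two of the three elements are minor at the planned size, and the interval point assumes normal quantiles, which the text suggests but does not state.

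A reader might infer more than the documents support:

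- **That baseline is ignored.** It is not; change from baseline is planned.
- **That the exact primary test contradicts the large-sample secondary methods.** It does not. GEE has no routine exact version; the exact test shows only that the small size was recognised.
- **That the QoL results would be invalid.** For a 1-df contrast the excess false positives are about one point. Only a joint test, which the plan neither names nor rules out, would be materially inflated.

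**Conclusion.** The point holds as a low-severity, nearly free improvement to secondary analyses of a feasibility pilot. The plan should say how the T0 score enters the GEE, because some models that fit its wording lose precision and one loses almost none. Under the four assumed correlation structures, complete data and 30 per arm, the variance reduction for the week 4-24 average is 36-60% against raw scores and 21-43% against change. These figures illustrate the possible loss; they do not estimate it for this trial.

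The interval shortfall is about one coverage point at n=30 and about two at an assumed n=17. The sandwich effect is mild for a 1-df contrast and about 12% against a nominal 5% for a joint 6-df test. The primary feasibility analysis is untouched. Handling of death and of dropout related to the scores is a separate matter and is not judged here.

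**What to change.** In Statistical methods, secondary objectives:

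1. Fit the GEE to post-baseline scores with arm, visit, arm-by-visit and the T0 score as covariate, and state the working correlation (for example exchangeable). Almost the same precision comes from keeping T0 as a response with the arms constrained equal there. Base the between-arm test on one 1-df contrast per score, such as the week 4-24 average, which matches the 6-month aim.
2. Use a small-sample variance, for example Mancl-DeRouen, with a t reference (for example, patients in the model minus 3 as df).
3. Use t-quantile intervals for per-arm, per-visit means and changes.

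**Cost.** Wording and modest programming in SAS or R, both already named; no new data. Intervals widen by about 4% at n=30 and 8% at n=17. The corrected test is slightly conservative for the average (3.7-4.4% in simulation). It gives up 2-7 points of power against the uncorrected test, part of which is that test's excess false positives. Patients with no post-baseline score do not enter the covariate model. For skewed scores, t intervals help only partly: at n=30, simulated coverage rises from 92.6% to 93.5%.
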